TMD	Temporomandibular disorder
TSG-DA	The Surgeon General, Department of the Army
USAMMDA	United States Army Medical Material Development Activity
USAMRMC	United States Army Medical Research and Material Command

4. Study Objectives

4.1. Primary Objective

The primary objective of this study is:

- To assess the safety and tolerability of KSL-W (30 mg dose) delivered in a chewing gum formulation compared with a placebo formulation during the 4 study days.

4.2. Secondary Objectives

The secondary objectives are:

- To assess the proof of concept (efficacy) using plaque re-growth [baseline minus Day 4 QHT score] of KSL-W (30mg dose) delivered in a chewing gum formulation compared to a placebo formulation.
- To evaluate the proof of concept (efficacy) of KSL-W (30 mg) in reducing plaque based on sub-scores from specific regions of the upper jaw, lower jaw, buccal and lingual surface based on the QHT.

5. Study Design

This is a Phase 2, double-blind, two-armed, placebo-controlled, randomized, single-center, multiple-dose study to evaluate the safety and proof of concept of KSL-W administered as a chewing gum formulation (APCG) 3 times per day over 4 treatment days, as outlined in [Table 2](#).

Table 2: Study Design

Treatment Day	Dosage * KSL-W / Placebo	# of Chews per Day **
Day 0	30 mg / 0 mg	3
Day 1	30 mg / 0 mg	3
Day 2	30 mg / 0 mg	3
Day 3	30 mg / 0 mg	3

* Subjects randomized to either KSL-W or placebo
**Each dose taken preferably after each meal (breakfast, lunch and dinner) or every 4-6 hours for a maximum of 3 chews per day

[Table 3](#) provides an outline of the study events and their timing.

Table 3: Study Event Schedule

			Study Visit/Day				
	Visit 1	Visit 2	Visit 3				Visit 4
	Screening (Day -18 to -14)	Screening (Day -10 to -8)	Day 0	Day 1	Day 2	Day 3	Day 4
General Procedures							
Written Informed Consent/HIPAA	X						
Evaluation Inclusion/Exclusion Criteria	X		X				
Demographic Data	X						
Medical History	X						
Vital Signs (BP, HR, RR Temperature)	X		X				X
Physical Exam		X					X ^a
Urine Drug Screen	X						
Urine Pregnancy Test	X ^b						X ^b
Periodontal Examination	X ^c						
Intraoral Exam (OHT, OST)	X		X				X
Oral Hygiene Check	X ^d		X ^d				X ^d
Randomization (1:1)			X				
Plaque Index Score	X		X ^e				X
Teeth Polishing			X				
Dispense Study Drug for Supervised and Unsupervised Use			X ^f				
Study Drug Administration			X ^g	X ^g	X ^g	X ^g	
Collect Used Study Drug			X ^h				X ^h
Electronic Diary Information System			X ⁱ	X ⁱ	X ⁱ	X ⁱ	
Adverse Event Reporting			X				X
Concomitant Medications	X		X				X
Study Discharge							X

BP=blood pressure, HIPAA=Health Insurance Portability and Accountability Act, HR=heart rate, RR=respiration rate, OHT=oral hard tissue, OST=oral soft tissue, QHT=Quigley-Hein Turesky Plaque Index

^aBrief symptom oriented physical exam (based upon reported adverse events)

^bPregnancy test for females of childbearing potential

^c Includes determination of number of teeth, score-able surfaces and pocket depths around teeth

^d Confirm subject has refrained from all oral hygiene procedures (flossing, brushing of teeth, mouth wash rinse) for 12 to 16 hours prior to Screening and Day 0 (Baseline). On Day 4, confirm subject has refrained from all oral hygiene procedures since chewing their last dose on Day 3.

^eMeasured after randomization, but before teeth polishing

^fSubject will be allocated 14 tablets of gum for the 4 day study period.

^gSubject will chew one tablet of gum for 20 minutes preferably after a meal (breakfast, lunch, dinner) or every 4 to 6 hours for a maximum of 3 chews per day. Chewing will be balanced as equally as possible between both sides of the mouth. The first tablet will be given under supervision in the clinic. Oral hygiene is not allowed at any time during the 4 day treatment. Oral hygiene cannot resume until after the determination of the Plaque Index Score on Day 4.

^h After each chewing period, the gum is disposed of in individual labeled bags. Subject records time/date of gum disposal on each bag. Subject will return all used/unused bags to the site on Day 4.

ⁱSubject records all start /stop times of gum chewing via the internet using the electronic diary information system (ePRO).

5.1. Randomization

A permuted block randomization list will be generated using SAS Version 9.3 (PROC PLAN) for the 15 active and 15 placebo blinded product vials. To maintain the blind, further details of the generation of the randomization list (block size) will be outlined in a separate Randomization Plan.

The unblinded statistician will send the randomization list to the following authorized product preparation staff at Salus Research in order for them to appropriately label the package materials with RANDOMIZATION NUMBERS according to Section 7.3.2 of the protocol.

[name] Salus Research [contact]

[name] Salus Research [contact]

[name]

Fort Wayne, IN 46825

In addition, the unblinded statistician will send the product preparation staff individual sealed security envelopes for each RANDOMIZATION NUMBER with the treatment assignment enclosed to be used only in the event of an emergency unblinding. These individual sealed envelopes containing the treatment assignment associated with each RANDOMIZATION NUMBER will be stored in a secured location only accessible to the unblinded product preparation staff.

Thirty-six subjects are projected to be screened at Visit 1 (Day -18 to -14) and Visit 2 (Day -10 to -8) and assigned a sequential SUBJECT NUMBER with the anticipation of enrolling 26 eligible subjects to obtain 24 subjects projected to complete the study. This SUBJECT NUMBER will be associated with the subject throughout the trial and linked to a separate RANDOMIZATION NUMBER to be assigned at randomization.

At Visit 3 (Day 0), each subject will be reevaluated by the next available evaluator for the study inclusion and exclusion criteria. If eligible and still consenting, the subject's vital signs will be

measured, an intraoral dental exam will be conducted (OST and OHT), the subject will be asked to confirm that he/she did not perform any oral hygiene procedures for 12-16 hours prior to Day 0. At this point the subject will be randomized and the evaluator will obtain the next available investigation product according to the randomization list from a central location that is easily accessible to both evaluators. The subject will then be considered randomized to the trial. This procedure will ensure that the next subject to be randomized into the trial will always receive the treatment corresponding to the next free number in the randomization list. After entering the RANDOMIZATION NUMBER as recorded on the investigational product into the eCRF, study procedures will continue with the supragingival assessment and each subject's teeth will be polished by a licensed dental hygienist. The first chew will then be supervised by the site study staff.

Breaking the blind (for a single subject) should be considered only when knowledge of the treatment assignment is deemed essential by the Principal Investigator. Procedures outlined in Section 7.3.3 of the protocol should be followed. Only the Principal Investigator or Sponsor can authorize emergency unblinding and the reason for unblinding should be clearly identified in the eCRF.

5.2. Blinding

For this double-blind study, the investigator, study biostatistician, staff not involved in product preparation, study subjects, and sponsor will be blinded to the treatment assignments throughout the duration of the study.

Salus Research will receive the investigational gum product directly from Fertin Pharma. Authorized product preparation staff at Salus Research will repackage the product into blinded individual opaque plastic vials in accordance with the randomization schedule. The product preparation staff will have no other responsibilities or involvement in the study. No other personnel are permitted in the preparation room during preparation of the blinded product.

The product preparation staff will receive a randomization schedule from the unblinded independent biostatistician. Each unique subject identification number will be assigned a treatment and this list will be used by the product preparation staff to prepare the blinded product. The blinded product will be labeled as shown in [Figure 1](#). Salus Research will be provided with individually sealed envelopes identifying each subject's specific treatment assignment. Salus Research will store these envelopes in a secure location accessible to the principal investigator in the event that the blind needs to be broken. The randomization, repackaging and labeling of the study product will be performed as per approved procedures in place at Salus Research.

Figure 1: Example Label for Blinded Product Vials

Subject ID Number:

Directions for Subject: Chew 1 tablet for 20 minutes balanced equally on both sides of the mouth. Each dose should be taken preferably after each meal (breakfast, lunch and dinner) or every 4-6 hours for a maximum of 3 chews per day.

Storage Instructions: Material to be stored at ambient room temperature, out of direct sunlight. Do not expose to extreme heat or cold.

Caution: New Drug – Limited by Federal (or U.S) law for investigational use.

Distributed by: Salus Research

Phenylketonurics: Contains Phenylalanine

KEEP OUT OF REACH OF CHILDREN

[name], Principal Investigator Study S-16-10

Emergency [contact]

Non-emergency [contact]

5.3. Procedures for Unblinding

Emergency unblinding of a subject should only be done in the case of a medical emergency, or in the event of a serious medical condition, when knowledge of the investigational study product is essential for the clinical management or welfare of the subject. In such an emergency situation, the Principal Investigator may unblind a subject's treatment without first discussing with the Sponsor's Safety Physician. While it is recommended to discuss with the Sponsor's safety physician prior to unblinding, the safety of the subject is the highest priority. The Sponsor will be notified by the Principal Investigator when emergency unblinding has occurred. Only the Principal Investigator or Sponsor can authorize emergency unblinding. The reason for unblinding should be clearly specified in the source documentation.

The individual treatment codes for each subject will be given to Salus Research in sealed envelopes. Each individual envelope will contain the subject identification number and their specific treatment assignment. These envelopes will be stored in a secure location accessible to the Principal Investigator in the event that the blind needs to be broken for emergency unblinding or individual emergency safety unblinding.

Contact Information for Emergency Unblinding:

Responsible person:

- Salus Research: [name],
[contact]

- Army: Acting-Director, Clinical Services Support Division
[contact]

5.4. Sample Size Justification

A sample size of at least 12 subjects per study arm (KSL-W, Placebo) is planned. This projection was based on certain results from the phase 2a trial (sponsor study number S-11-14). At Day 14, for the 30 mg dose ($n = 7$ subjects) the observed QHT mean change from baseline was 0.31 and for placebo ($n = 16$ subjects) the observed QHT mean change from baseline was 0.03. The observed QHT error standard deviation was 0.22. Using these results to form the basis of a prior joint distribution of means and error variance, a sample size of at least 12 subjects per study arm (KSL-W, Placebo) yields at least a posterior 94% chance of observing any KSL-W improvement in the sample mean QHT scores, and at least an 81% posterior chance (given that an improvement was observed) that the projected sample size for a similar, later phase, confirmatory study, using a 2-tailed $p = 0.05$, power = 90% criterion, is no more than 100 per study arm. It was assumed that these Day 14 results from phase 2a apply to this study having 4 days of treatment.

6. Statistical Procedures

6.1. Data Handling Conventions

6.1.1. Study Analysis Populations

The Safety Population consists of all subjects receiving at least one dose of study medication. These will most likely be randomized subjects receiving study therapy at Visit 3 (Day 0). The safety population will be analyzed according to the treatment actually received (KSL-W or placebo).

The Full Analysis Set (FAS) is defined as all randomized subjects having Baseline and Day 4 QHT evaluations, with the Day 4 evaluation occurring on the morning following the last chewing gum treatment from the previous day. The FAS population will be analyzed according to their randomized treatment assignment. A randomized subject with a missing Day 4 QHT whole mouth score will not have this score imputed, and will not be in the FAS cohort.

The Per Protocol Population (PP) is a subset of FAS and consists of all subjects with no major protocol violations itemized as follows: failure to obtain valid informed consent, accidental distribution of incorrect study medication, not following the inclusion/exclusion criteria, evidence that study medication was not taken, and the performance of oral hygiene other than chewing the study gum was during the study period, Day 4 evaluation performed later than on the morning following the last chewing gum treatment from the previous day. Analysis of the PP will be according to the treatment actually received by the subject.

6.1.2. Study Exposure

The baseline visit will be at Visit 3, Day 0, and the first dose of the study medication will be administered after randomization, determination of the baseline QHT score, and tooth polishing. The study exposure, in days, will be measured from Day 0 (date of randomization) to the last day

the subject was in the study. For subjects completing Visit 4, Day 4, the exposure will be 4 days (counting Day 0), regardless of whether the subject took any of the self-administered treatment. For early withdrawal subjects the study exposure will be from Day 0 to (and including) the subject's last day when the subject informs the study site of their early withdrawal. If the subject is lost to follow-up, the study site personnel will attempt to contact the subject to determine the day when they stopped study participation, and any adverse events that occurred during their self-administration time. Randomized subjects who are lost to follow-up and who are unable to be contacted will be assigned one day of study exposure, namely Day 0.

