6.2.4.4. Recording Adverse Events

Methods/Timing for Assessing, Recording and Analyzing Safety Measurements (Endpoints)

AEs and SAEs will be assessed at each study visit and documented in the source records. All AEs will be recorded on the eCRFs using accepted medical terms and/or the diagnoses that accurately characterizes the event. SAEs will be documented using the SAE paper form. It should be noted that the form for collection of SAE information is not the same as the AE eCRF. Where the same data are collected on both forms, the forms must be completed in a consistent manner. For example, the same event term should be used on both forms.

When a diagnosis is known, the AE term recorded on the eCRF will be the diagnosis rather than a constellation of symptoms. The investigator will assess and record for all AEs/SAEs: a description of the event (if the event consists of a cluster of signs and symptoms, a diagnosis should be recorded rather than each sign and symptom): onset date and time, and resolution date and time: intensity (recorded as mild, moderate or severe): relationship to study drug (recorded as unrelated, unlikely related, possibly related, probably related and definitely related): outcome (recorded as recovered, recovering, resolved with sequelae, not resolved, fatal, ongoing (end of study) or unknown if applicable): action taken with the study product (recorded as no action taken, dose reduced, interrupted, discontinued). When an event has not resolved by study closure, it will be documented on the AE eCRF as "ongoing."

The timeframe for the collection of AEs and SAEs for each subject begins at the first administration of investigational product (Visit 3, Day 0) through Visit 4, Day 4.

Duration of Follow-Up of Subjects after Adverse Events

Investigators are required to follow SAEs to resolution, even if this extends beyond the prescribed reporting period. Resolution is the return to baseline status or stabilization of the condition with the probability that it will become chronic. The SAE outcomes will be reported to the sponsor's representative using the Serious Adverse Event Report Form.

Investigators are not obligated to actively seek SAEs in former subjects; however, if an SAE, considered to be related to the investigational product is brought to the attention of the investigator *at any time* following completion of the study, the event will be reported to the

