7.1. Primary (Safety) Analyses

7.1.1. Adverse Events

A subject listing of deaths, other serious AEs, and discontinuations due to adverse events will be presented in tabular form by treatment received. Information will include a description of the event, the study day when the event was first observed, severity if applicable, relationship to study drug, resolution status of the event, subject status within the study (if applicable).

Summaries of adverse events by SOC only, and by event severity will be given by study arm. Separate tabular summaries by study arm, system organ class (SOC) and by preferred term (PT) within SOC will be given for:

- All AEs
- AEs possibly, probably, definitely related to study medication.

For each SOC and SOC, PT combination the estimated incidence proportions and estimated incidence rates will be given by treatment received.

The incidence proportion will be calculated as the number of subjects with a given treatment (KSL-W, placebo) having at least one AE with that SOC or SOC-PT classification, divided by the number of subjects with that treatment (expressed as a percent).

The incidence rate will be calculated as the number of adverse events with that SOC or SOC-PT classification divided by the total study exposure from all subjects with a given treatment. The study exposure is determined in days (see 3.1.2), but the total study exposure will be converted to subject-weeks. The total number of events and the rate in events per subject-week will be given. Since incidence rate takes into account exposure, this may be the measure more applicable to combine with other studies.

Subject listings of adverse events will include the verbatim AE terms as well as the SOC, PT. Severity, relationship with study drug, resolution of the event, and ongoing status of the subject within the study will also be shown in the subject listings, which will be presented by treatment and subject within treatment.

Adverse event data collected on paper forms will be described in the final Clinical Study Report and not displayed in a table or listing. This will include any additional maternal or paternal adverse events which will be collected on the Pregnancy Surveillance Form as well as any data collected on the Serious Adverse Event Form.

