If Yes was Urine Pregnancy Test performed? (Yes np/nw)		np/nw (%)		np/nw (%)	
If performed, Pregnancy Test result:	positive	n+/np (%)	n+/np (%)	n+/np (%)	
	negative	n-/np (%)	n-/np (%)	n-/np (%)	
Day 4					
Is the subject a woman of childbearing potential? (Yes nw/N %)		nw/N (%)		nw/N (%)	
If Yes was Urine Pregnancy Test performed? (Yes np/nw)		np/nw (%)		np/nw (%)	
If performed, Pregnancy Test result:	positive	n+/np (%)	n+/np (%)	n+/np (%)	
	negative	n-/np (%)	n-/np (%)	n-/np (%)	

Subject Listing: LREF07

(TREF07.2 FAS, TREF07.3 Per-protocol population)

Physical Exam pg 26 (screen), pg 76 (day 4)

PREGTEST pg 9 (screen), pg 77 (day 4)

TREF09

Concomitant Medication Summary

Safety Population: KSL-W (N=xx), Placebo (N=xx)

General Medication Category	Specific Medication	KSL-W		Placebo		Total	
		n/N (%)		n/N (%)		n/N (%)	
		xx (xx.x%)		xx (xx.x%)		xx (xx.x%)	
xxxxxx	(Total)	xx		xx		xx	
	xxxxxx	xx		xx		xx	
	xx xxxx	xx		xx		xx	
xxxxxx	(Total)						
	xxxxx						
	xxxx						

* n = Number of subjects with at least one use of the indicated medication or medication category. A subject may be counted more than once due to multiple medications used.

Subject Listing : LREF17

CMEDS pg 99 eCRF

TR10

Summary of Chew Compliance During Study Days 0, 1, 2, 3

Number and Percent of Subjects Performing Protocol Specified Chews

Safety Population: KSL-W (N=xx), Placebo (N=xx)

Study Day	KSL-W			Placebo		
	Chew 1 (Morning)	Chew 2 (Afternoon)	Chew 3 (Dinner)	Chew 1 (Morning)	Chew 2 (Afternoon)	Chew 3 (Dinner)
0	n (%)*	n (%)	n (%)	n (%)	n (%)	n (%)
1						
2						
3						

n = number of subjects with a date and time of starting the chew, % = 100*n/N

Subject listing of all chew occasions: LREF18: Chewing Documentation

TREF11

**Summary of Extent of Exposure and Adverse Event Incidence Proportion,
Rate**

Safety Population: KSL-W (N=xx), Placebo (N=xx)

	KSL-W	Placebo	Total
Total Exposure (subject-weeks)*	xx.x		
Number of Treatment Emergent Adverse Events	xx		
Estimated Incidence Rate (events/shj-wk)**	xx.xx		
Number of Subjects with at least one adverse event	xx		
Estimated Incidence Proportion (%)	xx.x		

* Time, in weeks, measured from the date of randomization to the date of last follow-up
**Number of events divided by the total exposure

Subject Listing: Exposure LREF12, LREF13 and Adverse events LREF15

Randomization date: RAND.RANDDT pg 36 eCRF

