Last follow-up : See SAP section 3.1.2 pgs 11-12. If subject completed the study then the last date is the date of Day 4 visit (VISITDT, pg 73 eCRF). If early withdrawal then last date is STATUS.WDRAWDT, pg 97 eCRF)

Adverse events from AES, page 100 eCRF tables and listings would come from ADaM adae after MeDRA coding.

TREF12

Summary of Serious Adverse Events , Discontinuations Due to Adverse Events, Deaths, Safety Population: KSL-W (N=xx), Placebo (N=xx)

	KSL-W	Placebo	Total
Number (%) of Subjects With Serious Adverse Events	xx (xx.x%)	xx (xx.x%)	xx (xx.x%)
Number (%) of Discontinuations Due to Adverse Events			
Number (%) of Deaths			

Subject listing of deaths, SAE's, and adverse event discontinuations: LREF16a, LREF16b
events from AES, page 100 eCRF tables and listings would come from ADaM adae after MeDRA coding.

Table TREF13

**Summary of Adverse Event Proportion, Rate by System Organ Class
All Treatment Emergent Adverse Events
Safety Population: KSL-W (N=xx), Placebo (N=xx)**

System Organ Class	KSL-W		Placebo			
	Number (%) [*]	Number of Events ^{**}	Event Rate (evt/sbj-wk) ^{***}	Number (%)	Number of Events	Event Rate (evt/sbj-wk)
xxxxx	xx (xx.x%)	xx	x.xx	xx (xx.x%)	xx	x.xx
xxxxx						

^{*}Number of subjects, n, with at least one event, and % is 100 n/N.

^{**}Total number of events from the given category

^{***}Total number of events divided by the total study exposure.

Subject listing: LREF16a

TREF14

Summary of Adverse Event Proportion, Rate by System Organ Class and Preferred Term
All Treatment Emergent Adverse Events
Safety Population: KSL-W (N=xx), Placebo (N=xx)

System Organ Class	Preferred Term	KSL-W			Placebo		
		Number of Subjects (%)*	Number** of Events	Event Rate (evt/sbj-wk)***	Number of Subjects (%)	Number of Events	Event Rate (evt/sbj-wk)
xxx	(Total)	xx (xx.x%)	xx	x.xx	xx (xx.x%)	xx	x.xx
	xxxx						
	xxxx						
	xxxx						
xxxxx	(Total)						
	xxxxx						
	xxxxx						

*Number of subjects, n, with at least one event, and % is 100 n/N.

**Total number of events from the given category

*** Total number of events divided by the total study exposure.

Subject listing LREF16a

Events from AES, page 100 eCRF tables and listings would come from ADaM adae after MeDRA coding0 eCRF and total exposure for event rate

TR^EF15

Summary of Adverse Event Proportion, Rate by Event Severity Safety Population: KSL-W (N=xx), Placebo (N=xx)

Severity	KSL-W		Placebo	

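### SAP 6.1.2 counts the last day for early withdrawals but not for completers, so the adverse-event rate denominator mixes two day-counting rules

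*SAP*

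**What the plan says.** SAP 6.1.2 opens with a general rule, "The study exposure, in days, will be measured from Day 0 (date of randomization) to the last day" the subject was in the study, and then gives rules by type of subject:

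- Completers: "For subjects completing Visit 4, Day 4, the exposure will be 4 days (counting Day 0", whether or not any self-administered gum was chewed.
- Early withdrawals: "For early withdrawal subjects the study exposure will be from Day 0 to (and including" the day on which the subject tells the site of the withdrawal.
- Lost subjects who cannot be reached: one day, Day 0.
- Lost subjects who are reached: the site asks when they stopped, but no explicit count is given.

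SAP 7.1.1 divides the number of events by total exposure: "The study exposure is determined in days (see 3.1.2), but the total study exposure will be converted to subject-weeks". It adds that this rate may be the better measure for combining with other studies. The TREF11 footnote defines exposure as "Time, in weeks, measured from the date of randomization to the date of last follow-up", and the programming note adds "If subject completed the study then the last date is the date of Day 4 visit". Neither says whether the end date itself counts. Both SAP 7.1.1 and that note send the reader to section 3.1.2 for the rule. SAP section 3 is the abbreviations list and has no such subsection; the rule is in 6.1.2.

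**The concern.** The completer rule and the withdrawal rule treat the last day differently. A completer's last day, Day 4, is left out; a withdrawal's last day is counted. The same calendar span can thus be worth different amounts of person-time. The clearest case is a subject who reports withdrawal on Day 4 without completing Visit 4: that subject gets 5 days and a completer gets 4.

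At stake is the denominator of a rate in the primary (safety) analysis, and one the SAP proposes for pooling. Pooling needs a stated and uniform measure of person-time. The rate is descriptive, and no test or decision rule depends on it.

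**Working it through.** **Inputs.** 26 enrolled, 13 per arm, to obtain 24 completers (Protocol 5.7). Exposure rules from SAP 6.1.2. Rates rounded to hundredths (SAP 10). *Assumption:* 2 subjects withdraw, both on Day k. The documents give no withdrawal day, so k = 0 to 4 is shown.

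**1. The plan's own figure.** Day 4 − Day 0 = 4 days. The completer value reproduces as elapsed days. It also equals the number of treatment days, Days 0 to 3.

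**2. Per subject.** Withdrawal as written: k + 1. Elapsed with a one-day minimum: max(k, 1).

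| Withdrawal on Day | 0 | 1 | 2 | 3 | 4 |
|---|---|---|---|---|---|
| As written | 1 | 2 | 3 | 4 | 5 |
| Elapsed, minimum 1 | 1 | 1 | 2 | 3 | 4 |

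The written rule adds one day per withdrawal for k = 1 to 4 and none for k = 0.

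**3. Whole trial.** Written: 24 × 4 + 2(k + 1). Elapsed: 24 × 4 + 2 × max(k, 1).

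| k | 0 | 1 | 2 | 3 | 4 |
|---|---|---|---|---|---|
| Written, person-days | 98 | 100 | 102 | 104 | 106 |
| Elapsed, person-days | 98 | 98 | 100 | 102 | 104 |
| Elapsed ÷ written | 1.000 | 0.980 | 0.980 | 0.981 | 0.981 |

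The difference is 0 to 2 person-days, at most 2.0%.

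**4. Both withdrawals in one arm** (11 completers + 2; the other arm has 13 × 4 = 52 days either way).

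| k | 0 | 1 | 2 | 3 | 4 |
|---|---|---|---|---|---|
| Written, person-days | 46 | 48 | 50 | 52 | 54 |
| Elapsed, person-days | 46 | 46 | 48 | 50 | 52 |
| Written rate ÷ elapsed rate | 1.000 | 0.958 | 0.960 | 0.962 | 0.963 |
| 1 event per subject-week, written / elapsed | 0.15 / 0.15 | 0.15 / 0.15 | 0.14 / 0.15 | 0.13 / 0.14 | 0.13 / 0.13 |
| 2 events per subject-week, written / elapsed | 0.30 / 0.30 | 0.29 / 0.30 | 0.28 / 0.29 | 0.27 / 0.28 | 0.26 / 0.27 |

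For k = 1 to 4 that arm's rate is 3.7% to 4.2% lower as written. After rounding it moves by 0 or 0.01. (Rate = 7 × events ÷ person-days.)

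**5. Is 1 or 2 events per arm plausible?** Phase 2a had 54 events, 64 enrolled and 58 completers over 28 days of dosing (Protocol 5.5.2), with a follow-up at Day 34 (Protocol 5.5.3). Its event-collection window is not stated, so both lengths are used.

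- 28 days: 54/(64 × 4) = 0.211 to 54/(58 × 4) = 0.233 per subject-week. Times 52/7 weeks, this is 1.6 to 1.7 events.
- 34 days: multiplying by 28/34 gives 1.3 to 1.4 events.

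The range of 1.3 to 1.7 supports the choice as an order of magnitude; it is not a forecast.

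**6. Everyone completes on time.** 13 × 4 = 52 days in each arm under either rule. Nothing changes.

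**The case against.** The strongest defence is that 4 days means the four treatment days, since SAP 5 describes gum taken "3 times per day over 4 treatment days, as outlined in" Table 2. Counted inclusively, those days reconcile a completer with withdrawals on Days 0 to 3. With withdrawals capped at 4 days the totals are 98, 100, 102, 104 and 104, so the written rule differs only at k = 4, by 2 days (104/106, or 1.9%). Much of this stands. A reader might infer that a Day 3 withdrawal tying with a completer is itself an error. It is not, because under this reading Day 3 is the last treatment day. The defence does not close the point, however: 6.1.2 defines exposure as time in the study, applies it regardless of gum taken, and puts no cap on the withdrawal rule.

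A reader might also infer that the completer's 4 days is a miscount for 5, since events are collected from "first administration of investigational product (Visit 3, Day 0) through Visit 4, Day 4". The documents do not support that. The first chew is the Day 0 breakfast chew in clinic (Protocol Table 6), and the last evaluation is on the morning of Day 4, so about four days elapse. Moving to 5 would change the convention for every completer without correcting an error.

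Nor is it clear that TREF11 contradicts 6.1.2 for a late Visit 4. The note points back to the SAP's exposure rule and then names date fields. For an on-time completer its date difference is also 4. Whether the fixed 4 days covers a Visit 4 held a calendar day late is arguable; the SAP simply does not say.

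Finally, the Day 4 case should be rare. Protocol 8.3.4 has the site try to bring withdrawn subjects back for the final visit (Visit 3 in the protocol, Visit 4 in the SAP).

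**Conclusion.** The inconsistency is real but narrow. SAP 6.1.2 applies one end-day rule to completers and another to early withdrawals, and no single convention stated there yields all its values. It is a matter of consistency at the lowest priority; the completer value of 4 days is sound.

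The sizes above rest on two withdrawals among 26 and on elapsed days with a one-day minimum as the comparator, a convention that the SAP does not itself state. The 4% figure further needs both withdrawals in the same arm, and the 0 to 0.01 shift needs 1 or 2 events there. Incidence proportions do not use exposure, and the plaque (QHT) analyses are untouched.

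**What to change.** State one formula for every subject, in SAP 6.1.2 and in the TREF11 footnote: exposure in days = last study date − Day 0 date, with a minimum of 1 day. This leaves on-time completers at 4 days and unreachable lost subjects at 1 day, and agrees with the TREF11 date fields. It also supplies a count for lost subjects who are reached, and counts a late Visit 4 by its actual date (one calendar day late gives 5). A withdrawal reported on Day 4 gets 4 days, the same as a completer. The price of the minimum is that Day 0 and Day 1 withdrawals both get 1 day.

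Name the convention beside the reported rates, and change 3.1.2 to 6.1.2 in SAP 7.1.1 and in the TREF11 note.

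The cost is a few sentences, two cross-reference corrections and trivial programming. Only non-completers and late visits can change. If outputs have already been produced, SAP 8 allows the change to be explained in the statistical and clinical study reports.
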